1.5. Study Hypotheses

Based on the study main problem, objectives, and literature review, three main hypotheses are constructed in order to test the relationship between the study variables.

These hypotheses are listed in this section as follows:

1. There is a statistically significant difference in serratiopeptidase, when used in addition to conventional drugs, in reducing post-operative pain, trismus, and facial swelling compared to conventional drugs alone following impacted third molar surgery.
2. There is a statistically significant difference in escin, when used in addition to conventional drugs, in reducing post-operative pain, trismus, and facial swelling compared to conventional drugs alone following impacted third molar surgery.
3. There is a statistically significant difference in serratiopeptidase in reducing post-operative pain, trismus, and facial swelling compared to escin, when

both used in addition to conventional drugs, following impacted third molar surgery.

Chapter 2:

Literature Review

2.1.Impacted Third Molar

The third molars, commonly known as wisdom teeth, often lead to complications during eruption, presenting a frequent concern in oral surgery (Wray et al., 2003). (Lytle, 1979) defines an impacted tooth as “*a tooth that has failed to erupt into its normal functional position beyond the time usually expected for such appearance. Eruption may have been prevented by adjacent hard or soft tissue including tooth, bone, or dense soft tissue*”. Among impacted teeth, mandibular third molars are the most common, followed by maxillary third molars and maxillary canines. Most unerupted teeth are extracted due to pain or infection, but other reasons include involvement in pathologies like cysts or tumors, causing resorption of adjacent teeth, or interfering with surgical procedures (Undrell Moore, 2011).

2.1.1. Etiology of Impaction

Several theories attempt to explain the cause of impacted wisdom teeth, as outlined by (Varghese, 2021). The most widely accepted include:

1. Disparity in tooth size and arch length: The jaw size may be insufficient to accommodate the wisdom teeth, leading to impaction.
2. Differential root growth: The uneven growth of mesial and distal roots can hinder eruption.
3. Delayed dental development: The wisdom teeth's development may lag behind skeletal growth, preventing proper eruption.
4. Decreased molar extractions: Early dental interventions and increased awareness have led to fewer extractions of permanent molars, resulting in less space for wisdom teeth.

2.1.2. Classification of Impaction

The core classification system of impacted third molars is the foundation for understanding their diverse clinical presentations and facilitating successful transalveolar extraction. This system helps categorize impacted teeth based on several key factors, outlined by (Bhargava, 2022):

1. Winter's classification (developed in 1926) focuses on the angulation of the impacted third molar relative to the long axis of the adjacent second molar ((Yilmaz et al., 2016)).
2. The Pell and Gregory classification system, proposed in 1933, assesses the position of impacted third molars based on two key factors: depth and the availability of space (Jaroń & Trybek, 2021).
3. Rood's criteria, proposed by Rood and Shehab in 1990, focuses on radiographic features indicating a close relationship between the impacted third molar and the mandibular canal (Rood & Shehab, 1990).
4. (Maglione et al., 2015) proposed a classification system specifically designed for evaluating impacted third molars using cone-beam computed tomography (CBCT) images.

2.1.3. Indications and Contraindications for Removal of Impaction

Several indications justify the extraction of wisdom teeth, as outlined by (Wray et al., 2003) in Table 2-1, including pericoronitis, infection, cystic change, etc. While extraction is the common course of treatment, there are situations where it may be contraindicated, as outlined in Table 2-2, such as high risk of damaging important structures, poor systemic health, or possibility of non-surgical treatment (Chiapasco et al., 2018).

Table 2-1 Indications for Removal of Impacted Third Molars.

Indications		Description
Infection	Pericoronitis	If the first episode is very acute or there has been more than one episode.
	Untreatable caries, pulpal or periapical pathology	The patient is unable to clean the distal aspect of the second molar or the area around the wisdom tooth, which is often partially erupted. This leads to the accumulation of food debris and plaque and then caries of the adjacent tooth surfaces.
	Periodontal disease	As a result of the unsatisfactory relationship between the second and third molars, the area is prone to periodontal disease, which may compromise the second molar.
Cystic change		When third molars are unerupted they may be the source of a dentigerous cyst, which can enlarge considerably before giving rise to symptoms.
External or internal resorption		External resorption of the second molar due to pressure from the unerupted third molar. Internal resorption within the wisdom tooth
Wisdom tooth in tumour resection		If an impacted wisdom tooth is associated with a tumour at the angle of the mandible, or is within the tumour resection margins.
Transplantation		When a patient presents with a heavily restored or carious first molar tooth and a partially erupted third molar tooth it is possible to transplant the third molar into the socket of the first molar.
Fractured mandible		If a fracture of the mandible through the angle occurs, an opportunity may arise to remove the third molar when surgical access is being made to treat the fracture itself.
Atrophic mandible		Third molar in an already atrophic mandible might be a potential site for fracture
Denture or implant design		To facilitate denture design or the accurate placement of implants.
Access to dental care		Where patients are in a situation where they do not have easy access to dental care
Medical condition		Removal of third molars following radiotherapy increases the likelihood of the development of osteoradionecrosis. Prior to cardiac surgery is another example.
Orthodontic considerations		To prevent or reduce imbrication of the incisor teeth.
Orthognathic surgery or reconstructive surgery		When orthognathic surgery is being planned, particularly with procedures such as sagittal split osteotomy.

Indications	Description
Age of patient	For young fit patients and not leaving them until an older age when the bone is denser and more difficult to manage, and when the patient may have medical problems related to older age group.

Table 2-2 Contraindications to Extraction of Impacted Third Molars.

Contraindication	Description
High risk of damaging important anatomic structures	A CT scan is mandatory to check the relationships between the impacted tooth and the involved anatomic structures
Compromised systemic conditions and age of the patient	
It can be removed for patients with a partially compromised systemic condition under the following notes:
 
 1. close cooperation with the specialist in charge of the patient 2. perform surgical intervention in a protected environment (e.g., hospital), 3. the possibility to monitor the patient's vital signs. 4. assistance from an anaesthetist/intensive care doctor. 
In elderly patients, this type of surgery can be more invasive due to the higher risk of tooth ankylosis.

Possibility of surgical exposure and orthodontic treatment, or autotransplantation	In these cases, it's better to align the impacted teeth by the orthodontic treatment or autotransplantation rather than removal.
Poor patient compliance	When the patient is uncooperative

2.1.4. Techniques for the Removal of Impacted Third Molars

The typical operative plan for impacted third molar extraction entails five main stages: 1) Incision 2) Bone Removal 3) Tooth Sectioning 4) Delivery 5) Wound Closure. However, some additional methods are also mentioned, including sagittal split osteotomy, buccal corticotomy technique, lingual split bone technique, lateral trepanation technique, partial odontectomy/coronectomy, and removal after orthodontic extrusion (Varghese, 2021)

2.1.5. Complications of the Removal of Impacted Third Molars

Possible complications of third molar removal include nerve numbness (paresthesia), dry socket (alveolar osteitis), infections, bleeding, jaw fracture, bone infection (osteomyelitis), damage to neighboring teeth, exposed fat pad in the cheek, opening between the mouth and sinus cavity (oral-antral communication), displaced teeth, inhaled objects (aspiration), gum tissue damage (periodontal defects), and jaw joint problems (temporomandibular joint injury). The four most common complications are nerve numbness, dry socket, infections, and bleeding (Bouloux et al., 2007).

While pain, swelling, and trismus are expected following surgery, poor surgical technique can exacerbate these issues. Pain management relies on analgesics administered before anesthesia wears off. Persistent pain indicates potential infection or dry socket requiring follow-up. Transdermal patches have shown effectiveness for post-extraction pain (Bhargava et al., 2019). Trismus may arise from injury to the medial pterygoid muscle or inflammation/hematoma at the extraction site (Fragiskos, 2007). Proper patient selection and surgical skill can minimize risks.

2.2. Post-operative Treatment following Third Molar Surgery.

Following third molar surgery, a course of conventional medication is typically prescribed to manage pain, swelling, and infection. Pain management commonly involves NSAIDs like ibuprofen or naproxen (Bhargava et al., 2019), while antibiotics may be employed to prevent or treat infection (Malamed, 2019). Additionally, corticosteroids may be used to combat inflammation and reduce swelling (Undrell Moore, 2011). To ensure optimal healing and minimize discomfort, adhering to the prescribed medication regimen and following post-operative instructions are crucial (Wayland, 2024).

Emerging research suggests potential benefits for both enzymes and phytotherapeutic drugs in managing post-surgical pain and swelling. Serratiopeptidase, a proteolytic enzyme, has shown promise in reducing inflammation around teeth and implants, potentially offering similar benefits after third molar extraction (Sannino et al., 2013; Villafuerte-Nuñez et al., 2013). Escin, a phytotherapeutic drug derived from horse chestnut, exhibits potent anti-inflammatory properties, suggesting its potential in reducing post-surgical inflammation and swelling (Wang et al., 2009). Figure 2-6 summarizes and compares between both medicines as follows:

Feature	Serratiopeptidase	Escin
Chemical Structure	Zinc-containing protein (metalloprotease)	Mixture of triterpenic glycosides
Source	Enterobacterium Serratia	Horse chestnut seeds
Pharmacokinetics	Limited absorption through intestines, distributed to sites of inflammation	High concentrations in skin and muscle, minimal internal distribution
Pharmacodynamics	Anti-inflammatory, analgesic, fibrinolytic, anti-biofilm, wound healing	Anti-edematous, anti-inflammatory, venotonic
Administration	Oral tablets	Oral tablets, topical gels/creams
Dosage	10-60 mg/day (2000 units/mg)	20 mg/day (oral), 1-2 applications/day (topical)
Complications	Rare adverse reactions like Stevens-Johnson syndrome, esophageal ulcers	Hepatic injury, toxic nephropathy
Contraindications	Pregnancy, breastfeeding, hemophilia, liver/kidney dysfunction, concurrent use with antiplatelet drugs/anticoagulants/natural supplements	Pregnancy, breastfeeding, renal/hepatic impairment
Therapeutic Applications	Oral and maxillofacial surgery (post-operative pain/swelling), inflammation, infections, major surgeries, traumatic injuries	Chronic venous insufficiency, hemorrhoids, post-operative edema, cerebral/intracranial edema, gynecology, periodontitis

Figure 2-1 Serratiopeptidase vs. Escin: A Comparative Table.

2.3.Split-mouth Randomized Controlled Trials

Dental clinical trials offer two options for randomizing treatments: over individuals (mouth-level) or over sites within the mouth (site-level). The parallel-group design, where the same treatment is applied throughout the entire mouth, is the simplest and most commonly used approach. On the other hand, the split-mouth design involves random assignment of treatments to specific sites within the mouth. This design utilizes each person as their own control, allowing for more precise treatment comparisons

(Lesaffre et al., 2009). The split-mouth design was introduced by (Ramfjord et al., 1968) to compare the effectiveness of different periodontal therapies within each subject's mouth. The design divides the mouth into two halves, randomly assigning different treatments to each half.

The split-mouth design compares treatments within each patient, avoiding bias that may arise when comparing separate cases and controls. It eliminates inter-subject variability and produces reliable results (Kazancioglu et al., 2014; Lesaffre et al., 2007). Compared to between-patient designs, the split-mouth design offers increased efficiency, requiring fewer participants and resources while achieving similar results. However, it also presents the potential for carry-across effects, where the treatment on one side of the mouth influences the response on the other side (Hujoel & Loesche, 1990; Varma & Chilton, 1974). To estimate treatment effects in a split-mouth design, researchers make assumptions about carry-over effects. Common assumptions include no carry-over effect, complete carry-over effect, and partial carry-over effect. These assumptions cannot be tested within the study itself and rely on prior knowledge (Hujoel & DeRouen, 1992).

When choosing a split-mouth design, researchers should consider bias, recruitment challenges, efficiency, and statistical analysis. Careful evaluation of potential carry-over effects is crucial to avoid bias. Finding suitable patients with symmetrical dental conditions can be difficult, and statistical analysis requires more complex methods compared to whole-mouth designs (Hujoel, 1998). Controlling carry-over effects in split-mouth studies is challenging. Washout periods of at least three weeks between treatment applications can help mitigate carry-over effects by allowing the body to eliminate residual effects of previous treatments (Gozali et al., 2017). Understanding the advantages, limitations, statistical considerations, and implications of the split-mouth design is essential for researchers in both the statistical and clinical fields. This knowledge

enables effective utilization of the design while acknowledging its potential drawbacks (Lesaffre et al., 2009).

Chapter 3:

Material and Methods

3.1. Study Design

This clinical trial will utilize a split-mouth design, randomly assigning two different treatments to each half of the patient's mouth. From this randomized study which is characterized by a triple-blind study, the procedures are going to be performed by qualified and experienced professional. However, the operator will have no access to data evaluated. The evaluator will have access to all responses of the symptoms of patients and will not know the treatment that is going to be selected, while the patient is unaware of which treatment or intervention is being applied to each side of their mouth. This stringent blinding approach minimizes potential biases and significantly enhances the scientific validity of the study.

Patients will be assigned into two groups and each patient acted as their own control using the split-mouth technique. One impacted third molar will be removed from one side and will receive conventional drugs while the other side will be removed after 3 weeks (wash-out period) and receive additional treatment beside the conventional drugs (i.e., either enzyme or herbal). The two groups will be classified as follows:

- The first group will receive conventional drugs with 10mg oral serratiopeptidase at immediate post-operative time and three times a day for post-operative five days on the first surgical visit and on the second surgical visit (after 3 weeks) conventional drugs will be given only or vice versa.
- The second group will receive conventional drugs with 20mg oral escin at immediate post-operative time and three times a day for post-operative five days on the first surgical visit and on the second surgical visit (after 3 weeks) conventional drugs will be given only or vice versa.

The conventional drugs, it will be administered to patients in the two groups, includes: Amoxicillin 500mg Cap b.i.d., Metronidazole 500mg Tab t.i.d., Diclofenac sodium 50mg Tab b.i.d.

3.2.Study Population

The study population will include patients who will visit the dental clinics in the College of Dentistry, University of Science and Technology, Yemen (USTY) for impacted mandibular third molars extraction during 2024.

3.3.Sample Size

The sample size is the number of participants planned to be included in the trial, usually determined using a statistical power calculation (Zanatta et al., 2017). This study determined the sample size using a power calculation based on previous research by (Costa et al., 2015). Their study found that preemptive use of etoricoxib 120mg significantly reduced the need for rescue analgesic medication compared to a placebo (1.6 ± 1.3 vs 4.0 ± 2.5). To achieve a power of 80% and a confidence interval of 95%. The study will need to evaluate 11 surgical sites per sub-group (<http://www.openepi.com/SampleSize/SSMean.htm>). To account for a potential 20% drop-out rate, a total of 14 sites per sub-group will be recruited. This will result in a total sample size of 56 dental units (2 teeth per patient) from 28 patients. The following Table 3-1 illustrates the study sample size and the planned treatment.

Table 3-1 : Sample Size and Study Treatment.

Groups	I		II		Total
Patients	14		14		28
Sub-groups	Control 1	Study 1	Control 2	Study 2	4
Sample size	14	14	14	14	56
Conventional Treatment	Amoxicillin 500mg Cap b.i.d		Metronidazole 500mg Tab t.i.d		N/A
	Diclofenac sodium 50mg Tab b.i.d				
Study Treatment	N/A	Serratiopeptidase 10mg t.id	N/A	Escin 20mg t.id	N/A

3.4.Sample Selection

Patients who will undergo to surgical removal of the impacted third molar will be assessed for their eligibility to participate according to the following inclusion and exclusion criteria:

Inclusion criteria:

- Medically fit patients.
- The presence of two asymptomatic mandibular third molar indicated for surgical extraction.
- Absence of pericoronitis or signs of inflammation during the last 30 days

Exclusion criteria:

- Patient administered other drugs such as NSAIDS and steroids.
- Patient has allergy to the drugs used in this study.
- Pregnant patient or a patient with lactation.
- Immunocompromised patients with diabetic or hypertension (from patient's history).
- Patients with irradiated maxillofacial region.
- Intellectually disabled patients and patients unable to come for follow up visits.
- Patients with acute and subacute pericoronitis

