3.5. Randomization

This clinical trial will utilize simple randomization based on the technique described by (Oliveira et al., 2021). This method involves drawing envelopes to determine the following:

- Surgical site: Test or control side
- Tooth: Right third molar ("A") or left third molar ("B")
- Surgery order: First or second session

The following steps of randomization will be followed:

1. Draw the tooth: An envelope is drawn to determine which third molar will be extracted first (right or left).
2. Draw the intervention: A second envelope is drawn to determine whether the selected tooth will receive the test intervention ("X-1") or no intervention ("X-2").
3. Draw the surgery order: A final envelope is drawn to determine whether the selected tooth will be extracted in the first or second surgery session.

3.6.Pre-operative and Post-operative Assessment

Prior to surgical removal of impacted third molar, preoperative variables (i.e., pain, trismus, and facial swelling) will be taken for each patient and recorded in the data collection sheet. Furthermore, the same post-operative variables (preoperative variables) will be taken immediately after the procedure, 2nd day, 3rd day and 5th day after the operation. Both pre-operative and post-operative variables will be done by the same measurements.

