3.6.1. Assessment of Pain

Measurements of this outcome will consider pain intensity based on Figure 3-1. Preoperative and postoperative pain intensity will be assessed using a standardized 10-centimeter visual analogue scale (VAS), ranging from 0 (no pain) to 10 (worst possible pain) (Sirintawat et al., 2017). Prior to surgery, patients will receive thorough instructions on using the VAS to accurately self-report their pain. Following the procedure, they will record their pain scores on a standardized form and return it to the researcher on the day of suture removal, allowing for continuous monitoring and evaluation of pain management effectiveness (Costa et al., 2015).

[figure not shown]

Figure 3-1 Pain Intensity Measurement.

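### Section 3.1 calls the trial triple-blind with an unaware patient, but the control session has no placebo and no procedure protects the evaluator's masking

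*Combined protocol and SAP*

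**What the plan says.** Section 3.1 describes the trial as triple-blind and makes three statements about masking.

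- Patient: "while the patient is unaware of which treatment or intervention is being applied to each side of their mouth".
- Evaluator: this person sees the patients' responses and "will not know the treatment that is going to be selected".
- Operator: "the operator will have no access to data evaluated".

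It concludes: "This stringent blinding approach minimizes potential biases and significantly enhances the scientific validity of the study".

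The same section then sets out the treatments. One session adds oral serratiopeptidase (first group) or escin (second group) to the conventional drugs, immediately after surgery and three times a day for five days. For the other session, "on the second surgical visit (after 3 weeks) conventional drugs will be given only or vice versa". Table 3-1 in section 3.3 enters N/A as study treatment for both control sub-groups, and step 2 of section 3.5 describes the control allocation as no intervention.

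Pain is self-reported on a visual analogue scale. Under section 3.6.1, after the procedure "they will record their pain scores on a standardized form and return it to the researcher". The Appendix A case sheet holds, for each visit, a group field (I or II) and a sub-group field (control or study), together with the grids for mouth opening, swelling and pain.

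**The concern.** The patient-blinding claim and the treatment description cannot both be true. A patient who takes an extra product after one operation and not after the other can see which session had the addition. A patient may not know the product's name, but the paired comparison in section 3.9 contrasts add-on with no add-on, and that is the contrast the patient can see.

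For the evaluator, the plan states an intention and no means. For the operator, lack of access to outcome data is not masking to allocation, so a third blinded party is not established either.

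Hypotheses 1 and 2 compare each add-on with conventional drugs alone. If patients expect the added product to help, their pain scores can differ between sessions even when the product does nothing. If the evaluator learns the allocation, the ruler and flexible-scale measurements are exposed as well. A report that followed the protocol would claim protection against bias that the design does not provide.

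**Working it through.** **1. The passages side by side**

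| Party | Claim in section 3.1 | What the rest of the plan provides |
|---|---|---|
| Patient | Unaware of the treatment on each side | Add-on in one session, conventional drugs alone in the other (3.1); N/A (Table 3-1); no intervention (3.5). No placebo, dummy or coded supply is described; a placebo is mentioned only for cited studies |
| Evaluator | Does not know the treatment | Not stated: who draws the envelopes, who dispenses, who holds the allocation, or that patients must not disclose. The allocation fields and outcome grids are in the same case sheet |
| Operator | No access to evaluated data | Nothing on whether the operator knows the allocation |

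**2. How visible the difference is**

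Scheduled oral doses per day, from section 3.1:

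- Control session: amoxicillin 2 + metronidazole 3 + diclofenac 2 = 7.
- Add-on session: 7 + 3 = 10.
- Extra doses over the course: 3 × 5 = 15, or 16 if the immediate dose is counted separately.

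The 10-versus-7 count applies on days when the conventional drugs are also being taken. The plan gives no duration for them.

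**3. The plan's own sample size**

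Section 3.3 uses 1.6 ± 1.3 versus 4.0 ± 2.5, 80% power and 95% confidence (two-sided 0.05):

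n = (1.3² + 2.5²) × (1.960 + 0.842)² / 2.4² = 7.94 × 7.849 / 5.76 = 10.82, rounded up to 11.

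11 / 0.8 = 13.75, rounded up to 14. Then 14 × 4 = 56 teeth from 28 patients. The stated figures reproduce. They are not in dispute, and they give 14 pairs per group, or 11 after the planned dropout.

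**4. What an expectation effect could do (hypothetical inputs)**

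The documents give neither an expectation effect nor an SD for within-patient pain differences. Assume an inert drug, a mean shift b in the paired difference of 0.5 or 1 point on the 0–10 scale, and a difference SD s of 2 to 3. The row for 1.5 shows how sensitive the result is. For the paired t test at two-sided 0.05:

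P(significant) = P(|T| > t₀.₉₇₅,ₙ₋₁), where T is non-central t with n − 1 df and non-centrality b / (s/√n).

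Critical values are 2.160 (n = 14) and 2.228 (n = 11). For example, b = 1, s = 2 and n = 14 give non-centrality 1 / (2/3.742) = 1.871 and probability 0.410.

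| s | b = 1, n = 14 | b = 1, n = 11 | b = 0.5, n = 14 | b = 0.5, n = 11 |
|---|---|---|---|---|
| 1.5 | 0.636 | 0.515 | 0.212 | 0.171 |
| 2 | 0.410 | 0.323 | 0.140 | 0.117 |
| 2.5 | 0.284 | 0.225 | 0.107 | 0.092 |
| 3 | 0.212 | 0.171 | 0.089 | 0.079 |

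The nominal rate is 0.050.

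**5. Hypothesis 3**

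Serratiopeptidase versus escin compares two add-ons. If the expectation shift is the same in both groups, it cancels in the difference of within-patient differences. The non-centrality is then 0, and a two-sample t test stays at 0.050 with 14 or 11 per group. Section 3.9 lists only paired tests, so this between-group test is itself an assumption.

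**The case against.** The patient contradiction is hard to dispute, but several points limit its reach.

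- **First session.** A patient who does not know what is being compared might record first-session pain without knowing whether it was the test or the control session. This depends on the information sheet and consent form (Appendices B and C), which are not in the reviewed text. The point stands: awareness is certain to be possible only by the second session. A placebo mentioned in those pages would contradict sections 3.1, 3.3 and 3.5, so a correction would be needed either way.
- **Evaluator.** Nothing in the plan contradicts the evaluator claim. The case sheet is a blank template, the allocation fields are in a separate block from the outcome grids, and they could be filled in after assessment. No passage says who completes them. This also stands: that the evaluator sees the completed fields is an inference. The plan still names no safeguard, and an unblinded patient could disclose the treatment.
- **Magnitude.** The false-positive rates follow from assumed inputs, take a uniform shift in the paired difference, and cover pain only, one of three outcomes. They illustrate the risk and do not measure it. The smaller shift shows what remains if the effect is weaker or affects only some sessions.
- **Control choice.** Conventional drugs without placebo are a legitimate comparator for an add-on question. That is accepted. The fault lies in the blinding claim.

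**Conclusion.** The concern holds and must be fixed. A headline property of the design is wrong as written: all 28 patients have one session with the add-on and one without, and nothing in the plan hides the difference. This conclusion rests on the text alone and needs no assumption about bias or SD.

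The consequence falls on Hypotheses 1 and 2, most directly on pain. Under the assumed 1-point shift and SD of 2 to 3, an inert add-on would reach significance in 41% to 21% of trials with 14 pairs and 32% to 17% with 11. Under a 0.5-point shift the figures are 14% to 9% and 12% to 8%. Hypothesis 3 is largely spared if the expectation effect is similar in both groups.

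Evaluator masking is unsupported rather than disproved. It matters because it is the protection that trismus and swelling can still have, and once lost it cannot be restored.

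**What to change.** Before any outcome is assessed:

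1. Take the group and sub-group fields off the case sheet and put them in a separate allocation log, kept from the evaluator until data lock. Name the role that holds the log; none is described now.
2. Instruct patients not to tell the evaluator what they are taking.
3. In section 3.1, replace the triple-blind label, the statement that patients are unaware and the sentence on stringent blinding with: evaluator-blinded, patient not blinded. State whether the operator knows the allocation.
4. Report pain as an unblinded, self-reported outcome whose add-on effect may include expectation.

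These steps are nearly free and leave the sample size, visits and treatments unchanged. The price is a less favourable design label. They do not remove the patients' expectation effect; they state it openly and protect the evaluator's measurements.

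If the sponsor wants to keep the patient-blind claim, a matching placebo in the control session is the alternative. That has a real cost: probably two matched products, one per group, and coded dispensing for 28 control sessions.
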